### 1.2.2. Clinical Summary

#### 1.2.2.1. Clinical Pharmacology

The pharmacokinetics (PK) of GED-0301 were characterized in a Phase 1 first-in-human study in subjects with active CD. The systemic bioavailability of GED-0301 following oral administration at dose levels up to 160 mg/day for 7 days to human patients is negligible.

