#### 1.2.2.2. Clinical Safety

Three clinical studies have been completed to date: [REDACTED], a Phase 1, dose-escalating, safety and PK study of 7 days of oral administration of GED-0301 in subjects with active CD, [REDACTED] a Phase 2 randomized, double-blind, placebo-controlled, dose-finding study of GED-0301 in subjects with active CD and [REDACTED], a Phase 2 randomized, double-blind, placebo-controlled, long-term extension study to evaluate the safety and tolerability of GED-0301 40 mg for the maintenance of CD in remission. [REDACTED]

[REDACTED] No deaths were reported during the conduct of the studies. No safety concerns that could modify the study conduct and/or investigational product (IP) administration arose from the studies.

Please refer to the IB for information concerning the available clinical studies and adverse event (AE) profile of GED-0301.

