### 1.3.3. Rationale for Dose, Schedule and Regimen Selection

Three oral dose regimens of GED-0301 versus placebo are being evaluated for the treatment of subjects with active CD:

- GED-0301 160 mg QD for 12 weeks; followed by placebo QD for 4 weeks; followed by alternating GED-0301 160 mg QD for 4 weeks and placebo QD for 4 weeks, until the Week 52 Visit;
- GED-0301 160 mg QD for 12 weeks; followed by placebo QD for 4 weeks; followed by alternating GED-0301 40 mg QD for 4 weeks and placebo QD for 4 weeks, until the Week 52 Visit;
- GED-0301 160 mg QD for 12 weeks; followed by continuous GED-0301 40 mg QD, until the Week 52 Visit.

The doses and dose regimens for this study were selected based on pre-clinical data and clinical data from the Phase 1 study [REDACTED] and the Phase 2 dose-finding study [REDACTED] in subjects with active CD.

The key considerations for the selection of the appropriate dose and dosing regimens were:

1. the very low systemic exposure in animals without signs of toxicity when given orally in doses at least 10 times higher, by body weight, than the proposed GED-0301 160 mg QD dose in humans;
2. the negligible systemic exposure of GED-0301 in humans;
3. the demonstrated efficacy of GED-0301 in Phase 1 and Phase 2 studies;
4. the similar safety profile of the various GED-0301 dose treatment groups in Study [REDACTED]; comparable numbers and types of TEAEs across all treatment groups, including the placebo treatment group were observed, with few SAEs or AEs leading to discontinuation of IP.

Study [REDACTED] demonstrated GED-0301 40 mg QD and 160 mg QD to be efficacious and safe after 2 weeks of treatment in subjects with steroid dependent or refractory CD.

Therefore, these data, in addition to the similar and favorable safety profiles of GED-0301 40 mg QD and 160 mg QD, provide supportive evidence for the selection of 160 mg QD as the initial dose of GED-0301 for a 12-week treatment induction of clinical remission and endoscopic response

[REDACTED]. The 12-week duration was selected in order to optimize therapeutic benefit, since it is expected that it would take a longer duration of treatment to achieve endoscopic benefit, such as endoscopic response, than to achieve clinical signs and symptoms benefit or clinical remission, in a moderate to severe CD population. Also, there is no consensus about the appropriate timing to assess the endoscopy evaluation, ranging from 10 to 26 weeks in different clinical studies

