**Table 3: Table of Events (Continued)**

|  | Screening Period | Double-blind Treatment Period |            |            |                 |            |            |            |            |            |            |            |            |            |                 | Follow-up Period |  |
|--|------------------|-------------------------------|------------|------------|-----------------|------------|------------|------------|------------|------------|------------|------------|------------|------------|-----------------|------------------|--|
| Visit Number   | 1 Screening      | 2 Baseline                    | 3          | 4          | 5               | 6          | 7          | 8          | 9          | 10         | 11         | 12         | 13         | 14         | 15              | ET a  | 16 b                              |
| Week   | -4               | 0                             | 4          | 8          | 12 c | 16         | 20         | 24         | 28         | 32         | 36         | 40         | 44         | 48         | 52 d | NA               | Follow-up                                    |
| (Visit Window)   | 28 days          |                               | (± 3 days) | (± 3 days) | (± 3 days)      | (± 3 days) | (± 3 days) | (± 3 days) | (± 3 days) | (± 3 days) | (± 3 days) | (± 3 days) | (± 3 days) | (± 3 days) | (± 3 days)      | NA               | 4 weeks after the last dose of IP (± 3 days) |
| Stool Assessment   | X                | -                             | -          | -          | -               | -          | -          | -          | -          | -          | -          | -          | -          | -          | -               | -                | -  |
| Clinical Lab (Hematology) g   | X                | X                             | X          | X          | X               | X          | X          | X          | X          | X          | X          | X          | X          | X          | X               | X                | X  |
| Clinical Lab (Coagulation) g  | X                | X                             | -          | -          | X               | -          | X          | -          | X          | -          | X          | -          | X          | -          | X               | X                | X  |

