| Clinical Lab (Chemistry) g  | X                | X                             | -          | -          | X               | -          | X          | -          | X          | -          | X          | -          | X          | -          | X               | X                | X  |
| Clinical Lab (Urinalysis) g   | X                | X                             | -          | -          | X               | -          | X          | -          | X          | -          | X          | -          | X          | -          | X               | X                | X  |
| Efficacy Assessments  |                  |                               |            |            |                 |            |            |            |            |            |            |            |            |            |                 |                  |  |
| Subject Diary h
Instruct use of electronic device/assess compliance | X                | X                             | X          | X          | X               | X          | X          | X          | X          | X          | X          | X          | X          | X          | X               | X                | X  |
| CDAI i  | X i   | X                             | X          | X          | X               | X          | X          | X          | X          | X          | X          | X          | X          | X          | X               | X                | X  |
| Ileocolonoscopy j   | X                | -                             | -          | -          | X               | -          | -          | -          | -          | -          | -          | -          | -          | -          | X               | X                | -  |

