In subjects who develop new changes in liver function tests (eg, ALT or AST > 2 x the upper limit of normal [ULN], or Total Bilirubin [TBL] > 1.5 x ULN with normal baseline values, or  $\geq 2$  x the baseline values in subjects with abnormal baseline values), repeat testing should be performed within 48 to 72 hours. If abnormalities persist, subjects should be evaluated for causes of new elevations in ALT/AST or TBL (including but not limited to tests for hepatitis, liver imaging, history of Gilbert's syndrome). If there are persistent elevations in ALT or AST and/or TBL then close observation (including laboratory testing as appropriate) should be initiated and treatment could be temporarily interrupted or discontinued. Discontinuation or temporary interruption of study treatment should occur when criteria delineated in [Appendix O](#) are met. After treatment discontinuation or interruption, assessments should continue until a return of aminotransferases and/or TBL to normal or baseline levels, or until alternative explanation for the abnormal liver function tests (LFTs) is found.

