### 7.2. Treatment Administration and Schedule

Subjects will receive GED-0301 (160 mg QD) or placebo during the first 12 weeks of the study, followed by one of 3 dose regimens of GED-0301 (40 mg QD or 160 mg QD) or placebo QD, until the end of the study (Week 52 Visit). All subjects will receive 4 tablets daily during the Double-blind Treatment Period. Matched placebo tablets will also be provided. Subjects will be instructed to take the IP in the morning, 30 minutes before breakfast, with a glass of water. Treatment and administration schedule are described in [Table 4](#).

Subjects who consent to participate in the PK substudy will be instructed to bring their IP to the study site where it must be administered after the collection of the predose PK blood sample. When the subject is providing a predose blood draw on the day of a PK substudy visit, the subject must be reminded to provide the date and time of his/her last dose from the day before the visit.

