## **APPENDIX O: CRITERIA FOR TEMPORARY INTERRUPTION OF IP OR STUDY DISCONTINUATION BASED ON LIVER FUNCTION TEST ABNORMALITIES**

Criteria for discontinuing or temporarily interrupting study treatment:

- When the baseline values were  $< 2$  x upper limit of normal (ULN), discontinue if alanine aminotransferase (ALT) or aspartate aminotransferase (AST) increases to  $> 5$  x baseline values.
- When the baseline values were  $\geq 2$  x ULN but  $< 5$  x ULN, discontinue if ALT or AST increases to  $> 3$  x baseline values.
- When ALT or AST increase  $> 2$  x baseline values AND the increase is accompanied by a concomitant total bilirubin (TBL) increase to  $> 2$  x baseline values.
- All patients who develop symptoms consistent with hepatic injury (eg, appearance of fatigue, nausea, vomiting, right upper quadrant pain or tenderness, fever, rash, and/or eosinophilia [ $> 5\%$ ]) in combination with elevations in liver enzymes.

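### No liver test is scheduled between Week 0 and Week 12, so the Appendix O rules have no routine result to act on during the 84 days of 160 mg daily induction

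*Protocol*

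**What the plan says.** **Liver rules.** Protocol Appendix O lists four criteria under the lead-in "Criteria for discontinuing or temporarily interrupting study treatment". Two use ALT or AST relative to baseline, one combines an enzyme rise with a bilirubin rise, and one combines symptoms with raised enzymes. Section 6.5.3 makes them operative: "Discontinuation or temporary interruption of study treatment should occur when criteria delineated in" Appendix O are met. It also asks for a repeat test within 48 to 72 hours of a new abnormality.

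**Where the values come from.** Section 6.5.3 places ALT, AST and total bilirubin in the serum chemistry panel. The hematology panel does not contain them.

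**When the panels are drawn.** In Table 3 the row beginning "Clinical Lab (Chemistry" is marked at Screening, Weeks 0, 12, 20, 28, 36, 44 and 52, Early Termination and Follow-up. Weeks 4 and 8 carry dashes. The row beginning "Clinical Lab (Hematology" is marked at every visit, including Weeks 4 and 8.

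**Dose in that interval.** Section 7.2 states: "Subjects will receive GED-0301 (160 mg QD) or placebo during the first 12 weeks of the study". All three active arms are on the same 160 mg daily dose until Week 12.

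**Reporting.** Clinically significant laboratory change is a secondary safety endpoint (protocol Table 2). SAP Section 12.3 summarises laboratory values by scheduled visit, adds a worst-value shift table and marked abnormalities over Weeks 0-52, and lists all laboratory data.

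**The concern.** A stopping rule works only if something produces the value that triggers it. The protocol treats a new liver abnormality as urgent enough to repeat within 48 to 72 hours, but that clock starts only after a first abnormal result. During induction no such result is scheduled until the period is over.

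Two things are at stake. For the subject, a rise without symptoms can continue on full-dose treatment until Week 12. For the results, the scheduled liver data for induction consist of one on-treatment time point. A rise that appears and resolves before Week 12 would leave no trace in the by-visit table, so an unremarkable Week 12 summary says little about the weeks before it.

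**Working it through.** The plan states no figure here to reproduce, so the check is the calendar and what follows from it.

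**1. Scheduled gaps.** Inputs: the Table 3 chemistry and hematology rows, with a visit window of ±3 days after baseline.

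| Panel | Scheduled weeks, 0 to 52 | Gaps |
|---|---|---|
| Chemistry | 0, 12, 20, 28, 36, 44, 52 | 12 x 7 = 84 days, then five of 8 x 7 = 56 days |
| Hematology | 0, 4, 8, 12, then every 4 weeks to 52 | 28 days throughout |

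With the windows, the first chemistry gap is 81 to 87 days and the later ones 50 to 62 days. Strictly between Week 0 and Week 12 there are 0 scheduled liver tests and 2 scheduled blood draws. The first gap is 84/56 = 1.5 times the later ones.

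**2. Match with dosing.** Section 6.2 puts visit evaluations before that day's dose, so the Week 0 value is pre-treatment and the Week 12 value closes induction. In Table 4 the alternating arms receive active drug in Weeks 16-20, 24-28, 32-36, 40-44 and 48-52, and chemistry falls at the end of each of those blocks. In the alternating 160 mg arm, later 160 mg dosing is therefore followed by a scheduled liver test after each 28-day block; induction is followed by one only after 84 days.

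**3. Wait for a persistent rise.** Assume onset is uniform over the 84 days and no unscheduled test is done.
- Current schedule: mean wait 84/2 = 42 days, maximum 84.
- With Weeks 4 and 8 added: mean wait 28/2 = 14 days, maximum 28.

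**4. Illustration for a transient rise.** If a rise lasts D days, with the same uniform onset, a scheduled test sees it with probability D/84 now and min(1, D/28) with the two tests added. The durations are assumptions; the documents give none.

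| Assumed D | Current schedule | With Weeks 4 and 8 |
|---|---|---|
| 14 days | 14/84 = 17% | 14/28 = 50% |
| 28 days | 28/84 = 33% | 100% |
| 42 days | 42/84 = 50% | 100% |

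These describe the visit calendar only. They are not estimates of how often liver rises occur.

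**The case against.** The strongest reply is that the prior risk is low and other routes to a test exist.

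**Low risk.** Section 1.2.2.1 says that systemic bioavailability "following oral administration at dose levels up to 160 mg/day for 7 days to human patients is negligible". Section 1.3.3 reports no signs of toxicity in animals at 10 or more times the human dose by weight, and Section 1.2.2.2 reports no safety concern from three completed studies that would change conduct. This stands, and it keeps the point small. It does not make the rules redundant: the protocol includes them, and it permits azathioprine, 6-mercaptopurine and methotrexate, for which Appendix H lists liver test abnormalities as a form of intolerance.

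**Other routes.** Section 6.2.1 allows an unscheduled visit whenever the investigator thinks it necessary, with every Table 3 assessment available, so a symptom is not strictly required. The differential count at Weeks 4 and 8 could show eosinophilia, which Appendix O names. Subjects who withdraw have chemistry at Early Termination. All of this is correct, but none of it is a routine liver test, and an isolated enzyme rise need not prompt any of them.

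**Reporting.** The SAP plans no inferential safety testing, and a reader can see that Week 12 is the first scheduled post-baseline value. That is fair; the loss is of information, not a false claim.

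Four stronger readings are tempting, and the documents do not support them.
- *The third and fourth Appendix O criteria carry no action.* They lack a verb of their own, but the lead-in and Section 6.5.3 apply discontinuation or interruption to all four.
- *The sponsor enters only after 4 missed days.* Section 7.6 concerns compliance. Section 11 allows discontinuation for a laboratory abnormality in the opinion of the investigator or the sponsor, with no day threshold.
- *160 mg has never been given for this long, or cumulative dose drives liver risk.* The visible text says an earlier study "demonstrated GED-0301 40 mg QD and 160 mg QD to be efficacious and safe after 2 weeks of treatment" and describes a "long-term extension study to evaluate the safety and tolerability of GED-0301 40 mg for the maintenance of CD in remission", but parts of these sections are redacted and they defer to the Investigator's Brochure. No passage links cumulative milligrams to liver risk.
- *Table 3 was forgotten when the liver guidance was added.* The amendment summary does not list Table 3 for that change, but this does not show an oversight.

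**Conclusion.** The point holds as a cheap improvement to the schedule. No routine ALT, AST or bilirubin result falls between Week 0 and the Week 12 Visit, an 84-day gap in the period when all active subjects (798 planned) are assigned 160 mg daily, against 56-day gaps later. The calendar fact needs no assumption beyond Table 3. The mean delays of 42 and 14 days assume uniform onset and no unscheduled test; the detection percentages also assume the duration of the rise.

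A reader might infer that the trial was unsafe or that the drug harms the liver. Neither follows: the documents report no hepatic signal and give no event rate. The SAP records that the study was terminated early. For data already collected, the practical consequence is that the by-visit liver tables for Weeks 0-12 should not be read as evidence that nothing happened before Week 12.

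**What to change.** In Table 3, add ALT, AST and total bilirubin at Weeks 4 and 8, taken from the blood draw already scheduled there for hematology. The longest scheduled gap in induction falls from 84 to 28 days.

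Cost: at most 2 x 1064 = 2128 extra panels, and no new routine visits. Any new abnormality would also trigger the 48 to 72 hour repeat in Section 6.5.3, which may bring a subject back outside a planned visit. If 2% to 5% of panels were flagged (an assumption), that is 0.02 x 2128 = 43 to 0.05 x 2128 = 106 repeat tests. Sample size is unaffected, and SAP Section 12.3 already summarises scheduled laboratory visits, so only its list of time points grows.

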### 4.2. Inclusion Criteria

Subjects must satisfy the following criteria to be enrolled in the study:

1. Subject is a male or female  $\geq 18$  years at the time of signing the informed consent form (ICF).
2. Subject must understand and voluntarily sign an ICF prior to conducting any study-related assessments/procedures.
3. Subject is willing and able to adhere to the study visit schedule and other protocol requirements.
4. Subject must have a diagnosis of CD with a duration of at least 3 months prior to the Screening Visit.
5. Subject must have ileitis, ileocolitis or colitis, as determined by ileocolonoscopy during screening.
6. Subject must have active CD disease, defined as a CDAI score  $\geq 220$  and  $\leq 450$  at screening.
7. Subject must have a 7-day average stool frequency  $\geq 3.5$  or abdominal pain  $\geq 1.5$  at screening.
8. Subject must have a total SES-CD  $\geq 6$  at screening, or the ileum segmental SES-CD  $\geq 4$  at screening.
9. Subject must have failed or experienced intolerance to at least one of the following: budesonide; systemic corticosteroids; immunosuppressants (eg, AZA, 6-MP, or MTX); or biologics for the treatment of CD (ie, infliximab, adalimumab, certolizumab or vedolizumab). (See [Appendix H](#) for details.)
10. Subject must meet the following laboratory criteria
  - a. White blood cell count  $\geq 3000/\text{mm}^3$  ( $\geq 3.0 \times 10^9/\text{L}$ )
  - b. Platelet count  $\geq 100,000/\text{mm}^3$  ( $\geq 100 \times 10^9/\text{L}$ )
  - c. Serum creatinine  $\leq 1.5 \text{ mg/dL}$  ( $\leq 132.6 \mu\text{mol/L}$ )
  - d. Aspartate aminotransferase (AST)/serum glutamic oxaloacetic transaminase (SGOT), alanine aminotransferase (ALT)/serum glutamic pyruvic transaminase (SGPT)  $\leq 2.5 \times$  upper limit of normal (ULN)
  - e. Total bilirubin  $\leq 2 \text{ mg/dL}$  ( $34 \mu\text{mol/L}$ ), unless the subject has a confirmed diagnosis of Gilbert's Disease
  - f. Hemoglobin  $\geq 8 \text{ g/dL}$  ( $\geq 4.97 \text{ mmol/L}$ )

- g. Activated partial thromboplastin time (APTT)  $\leq 1.5 \times$  ULN
11. Females of childbearing potential (FCBP) must have a negative pregnancy test at the Screening and Baseline Visits. While on IP and for at least 28 days after taking the last dose of IP, FCBP who engage in activity in which conception is possible must use one of the approved contraceptive options described below:

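### Appendix O's ALT/AST-alone stop level drops from just under 10 to 6 x ULN as baseline reaches 2 x ULN; secondarily, its combined ALT/AST and bilirubin criterion has no ULN minimum

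*Protocol*

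**What the plan says.** Protocol Appendix O lists four criteria for interrupting or discontinuing study treatment.

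- First, for a baseline below 2 x ULN: "discontinue if alanine aminotransferase (ALT) or aspartate aminotransferase (AST) increases to" more than 5 x baseline.
- Second, for a baseline of at least 2 but below 5 x ULN: the same rule at more than 3 x baseline.
- Third, a combined criterion with no baseline band and no mention of ULN: "When ALT or AST increase" more than 2 x baseline, "AND the increase is accompanied by a concomitant total bilirubin (TBL) increase to" more than 2 x baseline.
- Fourth, symptoms of hepatic injury "in combination with elevations in liver enzymes", with no enzyme level given.

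In the first two criteria ULN only selects the band. It sets no minimum for the on-treatment value.

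Section 6.5.3 supplies the earlier steps. For normal baselines it gives ALT/AST above 2 x ULN or total bilirubin (TBL) above 1.5 x ULN as examples of changes that call for a repeat test. For abnormal baselines the example is at least 2 x baseline. Persistent elevation calls for close observation, and "treatment could be temporarily interrupted or discontinued". The force of Appendix O comes from the next sentence: "Discontinuation or temporary interruption of study treatment should occur when criteria delineated in" Appendix O are met.

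Inclusion criterion 10d (Section 4.2) admits ALT and AST up to 2.5 x ULN.

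**The concern.** A stopping rule for liver enzymes should not become more permissive and then abruptly stricter as the starting value rises, unless a reason is given. Here it does. The change of multiple from 5 to 3 falls at a baseline of 2 x ULN, inside the range that the entry criteria allow, so subjects on both sides of it can be enrolled. Of two subjects with nearly equal baselines, the one with the slightly lower value may reach a much higher ALT or AST before Appendix O requires action on enzymes alone. The documents give no reason for this.

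Scheduled monitoring makes the level matter more. In the Table of Events (Table 3) the first on-treatment chemistry panel is at Week 12, and panels then follow every 8 weeks. A rise may already be large when first seen.

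The secondary concern runs the other way. The combined criterion is built only on multiples of baseline, so a subject with low starting values could meet it without any value leaving the normal range.

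**Working it through.** **Inputs** (all values in x ULN; b is the baseline)

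- Appendix O: multiple 5 for b < 2; multiple 3 for 2 ≤ b < 5; combined criterion at 2 x baseline for ALT/AST and for TBL.
- Section 4.2, criterion 10d: b ≤ 2.5 at entry.
- Section 6.5.3: example retest level 2b for abnormal ALT/AST baselines.

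The plan states no resulting stop level in ULN units, so there is no figure of its own to reproduce.

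**ALT/AST-alone stop level**

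Current level = 5b for b < 2, and 3b for 2 ≤ b ≤ 2.5. Capped level = the lower of 5b and 6 for b < 2, and 3b from 2 upward.

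| Baseline | Current stop, above | Example retest level | Stop with 6 x ULN cap, above |
|---|---|---|---|
| 1.2 | 5 × 1.2 = 6.0 | 2.4 | 6.0 |
| 1.5 | 5 × 1.5 = 7.5 | 3.0 | 6.0 |
| 1.75 | 5 × 1.75 = 8.75 | 3.5 | 6.0 |
| 1.99 | 5 × 1.99 = 9.95 | 3.98 | 6.0 |
| 2.0 | 3 × 2.0 = 6.0 | 4.0 | 6.0 |
| 2.25 | 3 × 2.25 = 6.75 | 4.5 | 6.75 |
| 2.5 | 3 × 2.5 = 7.5 | 5.0 | 7.5 |

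- Size of the step: just under 10 − 6 = just under 4 x ULN.
- Who is affected: the highest stop level among eligible baselines of 2.0 to 2.5 is 7.5. Setting 5b > 7.5 gives b > 1.5, so every baseline above 1.5 and below 2.0 has a higher stop level than any eligible baseline of 2.0 to 2.5.
- Where the cap bites: 5b > 6 gives b > 1.2. Below that nothing changes. From 1.2 to 2.0 the level is flat at 6, and it meets 3 × 2.0 = 6 with no step.
- In the capped band (1.2 < b < 2) the example retest level is 2b < 4, so the cap stays above it.

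**Combined criterion**

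The ALT/AST limb lacks the word *to* that appears in the TBL limb and in the first two criteria. It can be read as a level above 2 x baseline, or as a rise of more than 2 x baseline, which is a level above 3 x baseline. Write the limb as a level above kb, with k = 2 or 3.

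- ALT/AST can meet it while normal when kb < 1: b < 0.5 (k = 2) or b < 0.33 (k = 3).
- TBL can meet it while normal when 2b < 1: b < 0.5.
- Example under both readings: ALT from 0.3 to 0.95 (0.95 > 3 × 0.3 = 0.9) with TBL from 0.3 to 0.65 (0.65 > 2 × 0.3 = 0.6). Every value is normal and the criterion is met.
- Example above ULN but below both example retest levels: ALT from 0.6 to 1.85 (1.85 > 3 × 0.6 = 1.8) with TBL from 0.6 to 1.25 (1.25 > 2 × 0.6 = 1.2). A requirement that both values exceed ULN would still catch this case. A requirement at the Section 6.5.3 levels (2 and 1.5) would not.

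**The case against.** The best defence is that the ALT/AST-alone rule is a backstop. For baselines of 1.5 to 2.0 x ULN, repeat testing starts at about 3 to 4 x ULN. Persistent elevation then brings close observation and permits interruption or discontinuation. The combined and symptom criteria can act earlier, Section 11 allows discontinuation for any safety reason, and the DMC sees unblinded safety data. A subject would have to pass all of these before the difference between 10 and 6 x ULN mattered. This largely stands, and it limits the risk. A reader might infer from the step that such subjects go unprotected until nearly 10 x ULN; the documents do not support that. But the earlier steps are discretionary or need a further finding, so they leave the inversion in the required level.

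It is also fair to say that no text supports 6 x ULN as a liver safety limit in its own right. The case for it is consistency: it is the level the plan already sets at a baseline of 2.0.

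On the combined criterion, Appendix O's title speaks of abnormalities, and Section 6.5.3 of persistent elevations and of follow-up until values return to normal or baseline. Read as a whole, the plan hardly intends to stop a subject whose values are all normal. That makes the matter mainly one of drafting. It does not put a minimum into the criterion, and the ULN figures in Section 6.5.3 are only examples for retesting.

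Two stronger readings should be resisted.

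- A reader might infer that the first criterion also needs a floor, because a baseline below 0.4 x ULN reaches 5 x baseline below 2 x ULN. Stopping after a more than fivefold rise from the subject's own baseline is a defensible cautious choice. Loosening it is a trade-off, not a correction.
- A reader might infer that needless stops would distort efficacy through nonresponder imputation (Protocol Section 9.6.1; SAP Section 11.2.2.1). That would take withdrawal rather than temporary interruption, followed by missing Week 12 or Week 52 data. The number affected is not given, and the rules are the same in every blinded arm.

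**Conclusion.** The main point holds as an inconsistency in a safety rule. The ALT/AST-alone stop level falls by just under 4 x ULN at a baseline of 2 x ULN, and eligible subjects above 1.5 and below 2.0 x ULN have a higher level than any eligible subject at 2.0 to 2.5 x ULN. This follows from the text by arithmetic. It assumes only that baseline ALT/AST lies within the 2.5 x ULN entry limit; the step itself does not depend on that. The practical risk is reduced by the earlier steps, and the number of subjects in the affected band is unknown.

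The secondary point holds as a drafting gap: the combined criterion can be met with all values normal when TBL baseline is below 0.5 x ULN and ALT/AST baseline is below 0.5 x ULN (0.33 on the stricter reading). It leads to over-caution, not added liver risk.

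Both are for consideration. SAP Section 2 records that the study was terminated early, so the practical value now lies mainly in any later use of these criteria.

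**What to change.** 1. First criterion: for baselines below 2 x ULN, interrupt or discontinue when ALT or AST exceeds the lower of 5 x baseline and 6 x ULN. The downside is an earlier stop for baselines above 1.2 and below 2.0 x ULN. Add no lower floor to this criterion.
2. Combined criterion: keep the multiples of baseline, also require ALT/AST and TBL each to be above ULN, and word the ALT/AST limb as an increase *to* more than 2 x baseline. A stricter alternative uses the Section 6.5.3 levels (ALT/AST above 2 x ULN and TBL above 1.5 x ULN). Either minimum slightly lowers sensitivity at low absolute values, the stricter one more so. The symptom criterion stays as it is and can still be met below either minimum.

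The cost is amendment wording for two Appendix O criteria, with no added visits, samples or tests. Final thresholds belong to the sponsor's safety team.
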